6.1 Safety Endpoints

The safety and tolerability of AK002 will be assessed by determining the following:

- Adverse events (Section 13.1) including severity, withdrawals due to AE, and other safety parameters
- Adverse events of special interest (AESI), IRR, malignancy, and opportunistic infections (Section 13.3)
- Anti-drug antibodies (Section 11.5.4): Blood (serum) will be collected for assessment of ADA using a validated assay method. The ADA blood samples will be obtained at screening, predose on Days 1, 29, 57, 85, and additionally on Day 169 and Day 225 or 84 (± 3) days after last dose, if ET.
- Blood chemistry (Section 11.5)
- Hematology (Section 11.2.5)
- Urinalysis (Section 11.5.2)
- Physical examination (Section 11.3.2 and Section 11.3.5)
- Changes in vital signs (Section 11.3.7)
- Changes in concomitant medication use due to AE (Section 11.3.1)

6.2 Pharmacokinetic Endpoints

Blood (serum) will be collected for assessment of AK002 concentrations using a validated enzyme-linked immunosorbent assay (ELISA) method.

Pharmacokinetic (PK) blood samples will be obtained at screening, predose on Days 29, 57, 85, 113, and 141 and additionally on Days 8, 15, 169, 176, 197, and 225 or 28, 35, 56, and 84 (± 3) days after last dose, if ET. AK002 concentrations in serum will be used to calculate AK002 exposure.

6.2.1 Primary Efficacy Endpoints

To evaluate the efficacy and safety of 6 doses of AK002 in patients with moderate to severe EoD when compared with placebo. Efficacy will be evaluated by the following co-primary endpoints:

- 1) Proportion of tissue eosinophil responders at Week 24. A responder is a patient achieving a mean duodenal eosinophil count ≤ 15 cells/hpf in 3 highest duodenal hpf.
- 2) Change in TSS from baseline to Weeks 23–24 as measured by the PRO questionnaire.

The PRO TSS is comprised of 6 symptoms, as listed below:

- Abdominal pain intensity
- Nausea intensity
- Fullness before meal intensity
- Loss of appetite intensity
- Bloating intensity
- Abdominal cramping intensity

The severity and frequency of diarrhea and vomiting will also be collected on the PRO questionnaire but will not be included in the calculation of the TSS.

6.2.2 Secondary Efficacy Endpoints

To further characterize the efficacy of AK002 in patients with EoD as measured by:

- Change in tissue eosinophils from baseline to Week 24.
- Proportion of patients achieving mean eosinophil count ≤ 1 cell/hpf in 3 highest duodenal hpf at Week 24.
- Proportion of treatment responders at Weeks 23–24. A responder is defined as $>30\%$ improvement in TSS and mean eosinophil count ≤ 15 cells/hpf in 3 highest duodenal hpf.
- Proportion of patients who achieve $\geq 50\%$ reduction in TSS from baseline to Weeks 23–24.
- Proportion of patients who achieve $\geq 70\%$ reduction in TSS from baseline to Weeks 23–24.
- Change in weekly TSS over time.

6.2.3 Exploratory Efficacy Endpoints

To evaluate the effect of AK002 by comparing AK002 to placebo treatment for the following parameters:

- Change from baseline in **CCI** [REDACTED] over time.
- Changes in **CCI** [REDACTED] from baseline compared to post-treatment in the **CCI** [REDACTED] will be noted.
- Change from baseline in **CCI** [REDACTED] over time.
- Change from baseline in **CCI** [REDACTED] over time.

7. Patient Selection

7.1 Number of Patients

A total of approximately 80 patients will be dosed in the study in which 40 patients will receive 6 doses of 3 mg/kg AK002 and 40 patients will receive 6 doses of placebo every 4 weeks in a randomized, double-blind manner. All patients will be pretreated with 80 mg prednisone the day before the first infusion.

7.2 Number of Sites

Approximately 35 sites in the United States will participate in this study.

7.3 Study Population

Approximately 80 male and female patients with moderately to severely active EoD (without EG), aged ≥ 18 and ≤ 80 years, who fulfill the eligibility criteria specified below, will be enrolled into the study.

7.4 Inclusion Criteria

Patients are eligible to enroll in the study if all of the following criteria are met:

- 1) Provide written informed consent.
- 2) Male or female aged ≥ 18 and ≤ 80 years at the time of signing the informed consent for entry.
- 3) Baseline endoscopic biopsy with ≥ 30 eosinophils/hpf in at least 3 hpf in the duodenum as determined by central histology assessment of biopsies collected during the screening EGD without any other significant cause for the eosinophilia.
- 4) Completion of at least 4 daily PRO questionnaires per week for a minimum of 3 weeks during screening.
- 5) A weekly average score of abdominal pain, nausea, or diarrhea ≥ 3 on the PRO questionnaire (score from 0–10) for at least 2 weeks of screening and a weekly average TSS of ≥ 10 for at least 2 weeks of screening.
- 6) Inadequate or loss of response to, or intolerant to standard therapies for EoD symptoms, which could include PPI, antihistamines, systemic or topical corticosteroids, and/or diet, among others.
- 7) If patient is on pre-existing dietary restrictions, willingness to maintain dietary restrictions throughout the study.
- 8) Willing and able to comply with all study procedures and visit schedule including follow-up visits.

9) Female patients must be either post-menopausal for at least 1 year with FSH level >30 MIU/mL at screening or surgically sterile (tubal ligation, partial or total hysterectomy, or bilateral oophorectomy) for at least 3 months or, if of childbearing potential, have a negative pregnancy test and agree to use dual methods of contraception, have a partner who had a vasectomy, or agree to abstain from sexual activity from screening until the end of the study, or for 120 days following last dose of study drug, whichever is longer.

Non-vasectomized male patients with female partners of childbearing potential must agree to either abstain from sexual activity or agree to use a highly effective method of contraception from screening until the end of the study or for 120 days following last dose of study drug, whichever is longer. All fertile men with female partners of childbearing potential should be instructed to contact the Investigator immediately if they suspect their partner might be pregnant (e.g., missed or later menstrual period) at any time during study participation.

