5.1 Study Overview

This is a Phase 3, multicenter, randomized, double-blind, placebo-controlled study to evaluate the efficacy and safety of AK002 in patients with moderately to severely active EoD without EG who have an inadequate response with, lost response to, or were intolerant to standard therapies.

Patients enrolled in the study will receive 6 infusions of placebo or AK002 administered every 4 weeks and will be followed for 12 weeks after last dose unless patients elect to enter the optional open-label extension (OLE) period of the study.

Patients will be consented and then screened for 21–45 days prior to Day 1. Patients who meet all eligibility criteria can be enrolled into the study. Patients who do not meet all eligibility criteria at screening, or who qualify at screening but are not enrolled, may be assigned a new patient identification number and rescreened once. Patients rescreened within 30 days of signing the initial consent will not need to sign a new informed consent form (ICF) if no changes have been made to the ICF.

Patients will undergo EGD and colonoscopy with biopsy at screening and again 4 weeks after last dose. The EGD and colonoscopy should take place on the same day in order to minimize effects of procedure premedication on the PRO scores. For patients with a history of EoE and/or with a score of ≥ 3 on the dysphagia question on at least 1 day during screening, esophageal

biopsies will also be collected at screening and postdose. Biopsies from the gastric mucosa, duodenum, colon, and esophagus (as applicable) will be taken and reviewed by a central pathology reader. Additional biopsies will be collected for exploratory analysis.

The study is designed as follows:

- A screening period of 21–45 days with baseline evaluations for study eligibility, including active symptoms of disease (gathered by the patient reported outcome [PRO] questionnaire completed during screening) and EGD and colonoscopy (performed on the same day) with biopsy.
- Stool antigen test for *Helicobacter pylori* (*H. pylori*) will be assessed during screening to confirm no active *H. pylori* infection exists. If *H. pylori* is detected in tissue biopsies by the central pathologist, the patient should be excluded from the study.

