15.6 Efficacy Analysis

15.6.1 Primary Efficacy Endpoint Analysis

The first co-primary endpoint will be analyzed using Fisher's exact test. Patients who experience an ICE, i.e., exit the study prematurely or initiate prohibited or restricted medication, prior to end of Week 24 will be treated as non-responders. Proportion of responders and the associated 95% confidence interval (CI) will be presented for each treatment group. The between-group difference and the associated 95% CI will also be computed and presented. Sensitivity analysis may be carried out using the Cochran-Mantel-Haenszel (CMH) test stratified by the randomization stratification factor (baseline TSS <28 vs ≥ 28) to assess robustness of Fisher's exact test results.

The rationale for specifying Fisher's exact test for the primary analysis as opposed to specifying the CMH test is because when a stratum has 100% response for 1 treatment group and 0% response for another treatment group, the CMH test may lose efficiency or not be computable. This is evident from the Phase 2 study outcome.

The second co-primary endpoint will be analyzed using mixed model for repeat measures (MMRM) with treatment, week, treatment-by-week interaction, and baseline TSS-by-week interaction as fixed factors; gender and baseline TSS (continuous) as covariates; and study site (with pooling by geographic location) as random effect. If the model does not converge with pooled sites as a random effect, it will be simplified with pooled site as a fixed effect. Details about the method for pooling sites will be provided in the statistical analysis plan (SAP).

The weekly TSS is calculated as the average of the daily TSS. Weekly TSS will be set to missing if >3 daily TSS are missing. Baseline TSS will be the average of the last 2 weeks of daily TSS collected prior to the first infusion. The model variance-covariance matrix will be unstructured. However, if computation does not converge, the matrix will take the form of Toeplitz, autoregressive, or compound symmetry, whichever converges first.

Data on patients who experience an ICE, i.e., exit the study prematurely or initiate prohibited or restricted medications, prior to the end of Week 24 will be set to missing. If it is evident that the

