## 4. Definitions

### 4.1 Terminology and Definitions

**Table 2 Terminology and Definitions**

Terminology	Definition
Baseline	Baseline for non-daily assessment (e.g., laboratory tests and CCI) is defined as the non-missing value collected most recent to and before the time of the very first dose of study drug. This includes lab test collected on Day 1 Predose as an example. Baseline Total Symptom Score (TSS) will be the average of the weekly TSS collected in the last 2 weeks prior to the first dose. The day before and day of colonoscopy will be taken into consideration when computing baseline TSS.
Completer for the Study	Subjects who complete at least through the Day 176 visit if continuing to the OLE period of the study or Day 225 visit if not continuing to the OLE period of the study.
Concomitant Medication	Medication collected on the Prior/Concomitant Medication CRF, with end date on/after Study Day 1. Note a Prior Medication may also be a Concomitant Medication if the start date is prior to Study Day 1 and end date is on/after Study Day 1.
Enrolled	Subject who is randomized to a treatment group.
Newly Initiated Medication	Newly initiated medication refers to any medication with a start date $\geq$ Study Day 1
Patient-Reported Outcome	The patient-reported outcome (PRO) questionnaire evaluates 8 different symptoms with 10 daily questions for intensity and frequency: 
 
• Abdominal pain intensity
 
• Nausea intensity
 
• Vomiting intensity
 
• Vomiting frequency
 

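### Inclusion 4 does not tie diary completion to the two weeks that define baseline TSS, so a patient can be dosed with a thin or missing baseline for the second co-primary endpoint

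*Protocol*

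**What the plan says.** Inclusion 4 (Protocol synopsis and section 7.4, repeated in 10.2) requires "Completion of at least 4 daily PRO questionnaires per week for a minimum of 3 weeks during screening". On the length of screening, Protocol 5.1 says: "Patients will be consented and then screened for 21–45 days prior to Day 1". No section says that the compliant weeks must be consecutive or must be the last ones.

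The baseline is fixed to the end of screening. Protocol 15.6.1 states: "Baseline TSS will be the average of the last 2 weeks of daily TSS collected prior to the first infusion". SAP 6.11.4, which specifies the primary MMRM, uses practically the same wording. SAP Table 2 instead builds baseline from weekly scores: "Baseline Total Symptom Score (TSS) will be the average of the weekly TSS collected in the last 2 weeks prior to the first dose". The weekly rule is "Weekly TSS will be set to missing if >3 daily TSS are missing".

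I found no rule for a missing baseline TSS, or for a baseline with only one valid week. SAP 5.4.2 voids a two-week mean when one of its weeks is missing, but only for Weeks 23–24.

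**The concern.** Baseline TSS enters the second co-primary analysis twice: it is subtracted to give the change score, and it is a covariate on its own and by week (SAP 6.11.4). A patient without it contributes nothing to that model. The >30%, ≥50% and ≥70% TSS responder endpoints cannot be computed for that patient either. A pre-dose diary that was never filled in cannot be recovered later.

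Nothing else in the plan secures those two weeks:
- The Day 1 eligibility confirmation (Protocol 12.3) re-tests the same criteria, which name no weeks.
- The scheduled diary-compliance check first appears at Day 15 (12.6).
- The instruction to watch completion closely covers Days 155–168 only (11.2.1).
- Payment for completed diary weeks starts at dosing Day 1 (17.6).

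Screening beyond 21 days is foreseeable, because central histology and the parasite, *H. pylori* and *Strongyloides* results must all be available before dosing.

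**Working it through.** The plan gives no figure for diary compliance or missing baselines, so there is none to reproduce. The check has three parts.

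**1. Can it happen?** Count screening weeks forward from screening Day 1 (my assumption, since the Protocol does not define them) and take the last 14 days as the baseline window.
- 21 days: the three required weeks are all of screening, so both baseline weeks have at least 4 diaries, colonoscopy days aside.
- 22 days: the baseline weeks are days 9–15 and 16–22. Diaries on day 8, three of days 9–14 and four of days 16–21 leave 3 in the first baseline week. One week can fall short.
- 23 days: the baseline weeks are days 10–16 and 17–23. Diaries on days 1–4, on 8, 9, 10, 11, and on 15, 17, 18, 19 leave 3 in each. Both can fall short.
- 28 days: the baseline weeks are screening weeks 3 and 4. With three of four weeks compliant, only one can fall short.
- 32 days: the window starts on day 19. Days 15–18 supply the third week's 4 diaries, so the window can be empty. At 31 days it starts on day 18, which leaves only three days, so an empty window is not possible.

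**2. How often?** The documents are silent. Assume each week is compliant independently with probability p, over W whole weeks, and condition on at least 3 compliant weeks:
- lacking both = (1−p)² × P[Bin(W−2, p) ≥ 3] / P[Bin(W, p) ≥ 3]
- lacking at least one = 1 − p² × P[Bin(W−2, p) ≥ 1] / P[Bin(W, p) ≥ 3]

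| W | p | Lacking both | Lacking at least one |
|---|---|---|---|
| 5 | 0.9 | 0.01 × 0.729 / 0.9914 = 0.7% | 1 − 0.81 × 0.999 / 0.9914 = 18.4% |
| 6 | 0.9 | 0.01 × 0.9477 / 0.9987 = 0.9% | 1 − 0.81 × 0.9999 / 0.9987 = 18.9% |
| 5 | 0.7 | 0.09 × 0.343 / 0.8369 = 3.7% | 1 − 0.49 × 0.973 / 0.8369 = 43.0% |
| 6 | 0.7 | 0.09 × 0.6517 / 0.9295 = 6.3% | 1 − 0.49 × 0.9919 / 0.9295 = 47.7% |

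For W = 4, lacking both is 0%, since Bin(2, p) cannot reach 3. If compliance clusters by person (beta-binomial, mean 0.8–0.9), lacking at least one falls to 12–25% and lacking both is 1–3%.

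**3. What would it cost?** Of 80 patients, 0.7–6.3% is about 0.6 to 5, or at most 2.5 per arm. With the plan's difference of 7.4 and SD of 12.5, power = Φ(7.4 / (12.5√(2/n)) − 1.96). This gives 75.4% at n = 40, 74.4% at 39 and 73.3% at 38, about one point per patient lost per arm. The plan states 80% at 40 per arm. That discrepancy is a separate matter and does not bear on this point.

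**The case against.** The best answer is that SAP 6.11.4, the section that governs the primary model, averages daily scores. On that wording one diary in the window is enough, and only an empty window leaves no baseline. Protocol section 15 could even be read as the last two weeks with data. This stands, and it narrows the missing-baseline case. It does not remove it, because Table 2 of the same SAP uses weekly scores and so the SAP does not settle which applies. On the daily reading the baseline may rest on very few diaries, or on old ones.

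Protocol Table 2, note 1, lets Day 1 start as soon as the patient is eligible. That shortens screening for some patients but is permissive. Sites also review ePRO scores during screening (12.1) and could act under inclusion 8 or exclusion 22, but nothing directs them to look at the last two weeks.

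SAP 5.4.2 lists baseline TSS among its imputation variables. That data set feeds the sensitivity analyses in 6.11.5; SAP 6.11.4 does not tie it to the primary MMRM.

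**Conclusion.** The gap is real and modest. Under the plan as written, a randomised and dosed patient can have a thin baseline TSS, or none, in a co-primary analysis. On assumed compliance of 70–90% and 5–6 screening weeks, about 1–6% of patients meeting inclusion 4 lack both baseline weeks, and none do at exactly 4 weeks. These patients are lost under the SAP Table 2 reading. Under SAP 6.11.4 only those with an empty window are lost, and I have not estimated that share.

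Three stronger readings are tempting, and the documents do not support them.
- A reader might take the 18–48% lacking at least one week as lost. That figure includes those lacking both; by subtraction about 18–41% lack exactly one. No rule voids their baseline, so it is thinner, not missing.
- A reader might infer that the baseline must itself meet the TSS threshold. Inclusion 5 asks for "a weekly average TSS of ≥ 10 for at least 2 weeks of screening", again without naming weeks. Weekly scores of 10, 10 and 0 over 21 days qualify with a baseline of (10 + 0)/2 = 5, so a baseline below 10 is possible at any screening length. Its illustrative frequency is about 1–5% (0.3–2.2% with 3 weeks, 0.8–5.5% with 6, assuming mean TSS 28, between-patient SD 8–12 and week-to-week SD 3–8). Whether to add a floor is a design choice, and a floor adds selection on the value later subtracted.
- A reader might argue that a low baseline cannot show 7.4 points on top of the 11.5-point placebo fall in AK002-016, 18.9 in all. That fall is a group mean from a baseline of 27.57, not a constant for each patient. A floor of 10 would not cure it: with an assumed mean of 26, between-patient SD 10–12 and week-to-week SD 4–6, about 20% of eligible patients stay below 18.9 after the floor.

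**What to change.** Add to inclusion 4 and section 10.2: *including at least 4 questionnaires in each of the 2 weeks immediately before Day 1, not counting the day before and the day of colonoscopy*. Verify this in the ePRO system before the pre-Day 1 premedication step (Protocol 12.2) and before randomisation. A first check at the Day 1 visit would come after premedication has been taken. If the condition is unmet, defer Day 1 within the 45-day window. A TSS floor on the same two weeks is optional and is not part of this request.

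The cost is one clause and one ePRO check. Some Day 1 visits would move by several days. If the whole final week was empty and every later diary is completed, the delay is 11 days: 7 to refill the last week and 4 more to bring the earlier week to 4 diaries. A few patients near day 45 may screen-fail. If colonoscopy falls in the window and both of its excluded days lie in one week, that week needs 4 of 5 usable days.

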7.5 Exclusion Criteria

Patients will be excluded from the study if they meet any of the following criteria:

- 1) Use of systemic or topical corticosteroids exceeding the equivalent of 10 mg/day prednisone within 4 weeks prior to the screening visit.
- 2) Baseline endoscopic biopsy with ≥ 30 eosinophils/hpf in 5 hpf in the gastric mucosa as determined by central histology assessment of biopsies collected during the screening EGD.
- 3) Change in the dose of corticosteroids (systemic or topical), PPI, leukotrienes, or diet therapy within 4 weeks prior to the screening visit.
- 4) Treatment with any immunosuppressive or immunomodulatory drugs that may interfere with the study within 12 weeks prior to the screening visit.
- 5) Prior exposure to AK002 or known hypersensitivity to any constituent of the study drug.
- 6) Active *H. pylori* infection as confirmed by a stool antigen test for *H. pylori*.
- 7) History of inflammatory bowel disease, other chronic inflammatory diseases in the colon (with the exception of eosinophilic colitis), celiac disease, achalasia, or esophageal surgery.
- 8) History of bleeding disorders and/or esophageal varices considered to be significant by the Investigator.
- 9) Other significant causes of gastric and/or duodenal eosinophilia or eosinophilic granulomatosis with polyangiitis (EGPA).
- 10) Confirmed diagnosis of hypereosinophilic syndrome (HES).

- 11) Women who are pregnant, breastfeeding, or planning to become pregnant while participating in the study.
- 12) Presence of an abnormal laboratory value considered to be clinically significant by the Investigator.
- 13) Any disease, condition (medical or surgical), or cardiac abnormality, which, in the opinion of the Investigator, would place the patient at increased risk.
- 14) History of malignancy, except carcinoma in situ, early-stage prostate cancer, or non-melanoma skin cancers. However, patients with cancers that have been in remission for more than 5 years and are considered cured can be enrolled.
- 15) Treatment for a clinically significant helminthic parasitic infection within 6 months of screening.
- 16) Positive helminthic infection on ova and parasite (O&P) test.
- 17) Seropositive for *Strongyloides stercoralis* at screening.
- 18) Seropositive for HIV or hepatitis at screening, except for vaccinated patients or patients with past but resolved hepatitis, at screening. See [Appendix 12](#).
- 19) Vaccination with live attenuated vaccines within 30 days prior to initiation of treatment in the study, during the treatment period, or vaccination expected within 5 half-lives (4 months) of study drug administration. This exclusion criterion does not apply to all types and formulations of vaccines authorized by FDA or other regulatory authority for the prevention of COVID-19, which may be administered before, during, or after the study. The vaccine should not be administered within 7 days before and within 7 days after the administration of AK002 so that any side effects caused by either of the 2 medications can be more easily determined.
- 20) Participation in a concurrent interventional study with the last intervention occurring within 30 days prior to study drug administration (or 90 days or 5 half-lives, whichever is longer, for biologic products).
- 21) Known history of alcohol, drug, or other substance abuse or dependence that is considered by the Investigator to be ongoing and clinically significant.
- 22) Any other reason that in the opinion of the Investigator or the Medical Monitor makes the patient unsuitable for enrollment.

